The investigational pharmacy at Children's Mercy Hospital will coordinate with each site their purchase of the megestrol solution from the single manufacturer. All sites will use the exact formulation, containers, and instructions as specified by the lead investigational pharmacy.

Single IRB Review for a Multi-site study

KUMC will serve as the IRB of record for all sites. Procedures will be identical at all sites. Sites will all have an existing multidisciplinary feeding team that includes at least a pediatric healthcare provider (MD, DO, ARNP), Psychologist, Dietitian, and Occupational Therapist/Speech Pathologist.

The PI and study coordinator will have an orientation with each site prior to enrolling subjects. The study coordinator will be responsible for notifying all sites of amendments to the IRB and dissemination of current study documents (please see Multi-Site Communication Plan).

To minimize any differences across sites, the PI will travel to each site annually, and the team will meet together every year at the NASPGHAN meeting. Also, a weekly mandatory one hour phone conference will occur across all sites to discuss protocol implementation issues. The study coordinator will send communication to the PI and the Point of Contact (POC) at each site of any relevant study communication (please see Multi-Site Communication Plan).

Protocol compliance, problems, and adverse events will be discussed in the weekly multi-site conference call. Sites will be given written protocols during orientation that define protocol deviations, unanticipated problems, and adverse events, and the method to report those to the lead site.

Safety

For the treatment arm of the current study we are proposing to use medications off label. Therefore there is risk of unexpected negative results. We do not expect any negative outcomes, however, as these medications have been used safely in previous work (12,13). To monitor for these negative side effects,

CONFIDENTIAL

This material is strictly confidential and is intended solely for the guidance of clinical investigation. Do not disclose or use except as authorized in writing by the study sponsor

patients will be contacted weekly while taking the medication (via the Tele-visits described previously) for any negative gastrointestinal, behavioral, feeding, or other negative sequelae suspected to result from the medications. (If such patients are subjected to stress such as an infection or surgery, they may develop adrenal crisis. The patient suddenly becomes cyanotic and cold, blood pressure drops, and without immediate resuscitation the patient goes into shock). If any negative outcomes are identified they will be reported to our Data Safety and Monitoring Board and proper steps will be taken.

Under certain conditions children may removed from the study and treated clinically. The medical monitor and site PI will assess the case and determine if it is safe for the participant to continue.

Risk/benefit assessment:

Our previous work suggests that iKanEat is effective in moving children from tube to oral eating, and that amitriptyline does not improve the outcomes associated with the protocol. However, we do not know if the remaining medication (megestrol) improves the outcomes associated with iKanEat. As all medications have risks, it is necessary to test this remaining medication to determine if the risk is outweighed by the benefit the medication brings to the iKanEat protocol.

Data Safety Monitoring Board

For the current study we will have a Data Safety Monitoring Board that will review all subject safety data twice annually. DSMB will review protocol adherence, adverse events, unanticipated problems, voluntary and study team initiated withdrawals, etc. This team is available to the investigators at any time should an issue of safety arise, as was the DSMB for their previous study (HD068221). This board will be composed of [name], Professor of Pediatrics and [name], Professor, Rady Children's Hospital and UCSD. Twice annual conference calls will be held between the DSMB members and the investigation team to assure the best outcome for all subjects. Any serious adverse events will be reported immediately to the relevant institutional IRBs and to the DSMB.

Population(s) for Analysis. Our primary analysis will focus on a protocol-compliant population, but we will secondarily also analyses the all-treated population, as described below.

- All-randomized population: Any subject randomized into the study, regardless of whether they received study drug
- All-treated population: Any subject randomized into the study that received at least one dose of study drug
- Protocol-compliant population: Any subject who was randomized and received the protocol required study drug exposure and required protocol processing

8 Safety and Adverse Events

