1.4 Dose Rationale and Risk/Benefits

The dose of the megestrol was based upon the preliminary clinical data published.

CONFIDENTIAL

This material is strictly confidential and is intended solely for the guidance of clinical investigation. Do not disclose or use except as authorized in writing by the study sponsor

2 Study Aims

The primary aim of the current study is to conduct a randomized controlled trial of a 4-week course of megestrol, the only remaining medication that is part of the iKanEat protocol, to ensure that the addition of megestrol results in improved child outcomes. The second aim is to assess the safety of megestrol as part of the iKanEat protocol. Our previous work (as well as work by others) suggests that a 6 week course of megestrol can lead to adrenal insufficiency in some children (11-14), so as part of the current protocol, we will assess the safety of a 4 week course of this drug.

Finally, parents of tube fed children encounter multiple psychosocial stressors regarding tube feeding (15). These include concerns about their child's survival due to their underlying medical issues, feelings of "failure" due to their inability to feed their child orally (16), increased feelings of stress around the tube feeding (17) and decreased support from others due to the tube feeding (18,19). Our research indicates that quality of life can be poor in tube fed children (11), even more so than children with cancer or burns. Given the significance of these issues, the third aim of the study is to examine the effect of the transition from tube to oral feeding on parent stress and parent and child quality of life.

Aim 1: To assess the efficacy of megestrol as part of the 24 week iKanEat protocol.

Hypothesis 1: Children randomized to the megestrol group will be significantly more successful in making the transition to oral feeding (defined as obtaining at least 90% of calories orally) than children randomized to the placebo group.

Aim 2: To assess the safety of 4 weeks of megestrol as part of the 24 week iKanEat protocol.

Hypothesis 2A: Children randomized to the megestrol group will not differ from control children in morning cortisol classification level (low, average, high) and will remain within the normal range at all time points.

Analyses 2B: Exploratory analysis will determine which, if any, covariates (gender, age, and diagnoses at week 0, diagnoses at birth) are related to abnormal morning cortisol levels.

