5.4 Prior and Concomitant Therapy

All current therapies and medications will be allowed to continue throughout the study, except those listed in the exclusionary criteria section.

Parents will be educated that megestrol is a steroid, and what to do if their child becomes acutely ill and the treating provider prescribes a steroid. So, if the child is prescribed a steroid (oral or inhaled), the parents should consult with the treating physician to see if a non-steroidal option is available. If not, and the treating physician proceeds with steroids for medical reasons, the parent should contact the iKanEat study team to inform them of this prescription.

If the prescription is over 7 days, then the iKanEat medical monitor will review the case and decide how to proceed with the study drug. Options could include tapering off the study drug temporarily and to reactivate after the prescription is given; or, tapering early if the child is in the final weeks of study drug; or other options as deemed appropriate by the medical monitor.

If the prescription is 7 days or less, than the study team will note it in the REDCap Case Report Form and report it to the medical monitor, but no action will be taken.

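### Section 7 warns of adrenal crisis after infection or surgery, but both parent actions in 5.4 wait for an oral or inhaled steroid prescription and make no exception for suspected adrenal insufficiency

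*Combined protocol and SAP*

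**What the plan says.** **The hazard.** In Section 7, under Safety, the plan states: "If such patients are subjected to stress such as an infection or surgery, they may develop adrenal crisis". It describes the onset in these terms: "The patient suddenly becomes cyanotic and cold, blood pressure drops, and without immediate resuscitation the patient goes into shock". Section 2 adds that the team's earlier work, and that of others, "suggests that a 6 week course of megestrol can lead to adrenal insufficiency in some children"; Aim 2 exists to assess the safety of the 4-week course. Section 8.1 lists adrenal insufficiency, with its symptoms, among the expected events.

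**The parent rule.** Section 5.4 opens with "Parents will be educated that megestrol is a steroid" and says they will also learn "what to do if their child becomes acutely ill and the treating provider prescribes a steroid". If an oral or inhaled steroid is prescribed, "the parents should consult with the treating physician to see if a non-steroidal option is available". If there is none and "the treating physician proceeds with steroids for medical reasons", the parent informs the study team. For a course of 7 days or less, "the study team will note it in the REDCap Case Report Form and report it to the medical monitor", with no further action. The medical monitor reviews longer courses and decides how to handle the study drug.

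**The concern.** The hazard and the parent rule do not match. The Safety text names infection and surgery as triggers and describes a sudden emergency. The rule in 5.4 is triggered by something else, a steroid prescription, and its first step is to look for a way to avoid the steroid. That step may be sensible for an ordinary prescription during dosing. It is the wrong first question if the steroid is being given because the child may be adrenally insufficient.

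The children are medically complex, so a clinician outside the study may well be the first to see an acute illness. Treatment is blinded, and that clinician may not know that megestrol is a possibility. The parent is the obvious messenger, but 5.4 does not give the parent that message. Delay or discouragement of appropriate steroid treatment is what is at stake, in a situation the protocol itself describes as progressing to shock.

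**Working it through.** No power, rate or sample-size figure is involved, so the check sets the text side by side.

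**Step 1. Section 5.4, clause by clause**

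| Clause | Who acts | Condition |
|---|---|---|
| Parents are taught that megestrol is a steroid | Study team | None |
| Parents are taught what to do in acute illness | Study team | Acute illness and a steroid prescribed |
| Ask about a non-steroidal option | Parent | Oral or inhaled steroid prescribed |
| Tell the study team | Parent | Physician goes ahead with the steroid |
| Review, or note and report | Medical monitor or study team | Course over 7 days, or 7 days or less |

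Parent actions: 2. Parent actions that require a steroid prescription: 2. Exceptions for suspected adrenal insufficiency or steroid cover: 0. Mentions of surgery: 0.

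**Step 2. Cases run through the rule**

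- Child with a fever, no steroid prescribed: no parent action is triggered.
- Surgery planned, no steroid prescribed: no parent action is triggered.
- Oral steroid prescribed as cover, or for suspected adrenal insufficiency: the parent first asks for an alternative. The physician may still proceed, and the study team is then told.
- Injected steroid in an emergency: not expressly reached, because the rule names oral and inhaled steroids.

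**Step 3. Other safeguards, and whether they inform an outside clinician when the child is ill**

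- Normal morning cortisol before the first dose (6.4): predates exposure.
- Weekly tele-visits on drug that ask about illness (6.5 to 6.7; Section 7, Safety): useful, but a sudden event can fall between calls.
- Open invitation to contact the team (6.5 to 6.7): names no trigger and concerns the study team.
- Adverse-event questioning at each contact and 24-hour SAE reporting (8.2, 8.3.1): inform the investigator and sponsor.
- Post-treatment cortisol at least 5 days after the last dose (6.8), with endocrinology consulted after two abnormal results (3.4): comes after dosing and depends on laboratory results.
- Unblinding of providers after an SAE (6.11, 8.4): a possible route, discussed under the objection.

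None of these has the parent tell the treating clinician about possible adrenal suppression.

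**Step 4. Can the harm be sized?** No. The documents give no rate of intercurrent illness or surgery, and none of adrenal suppression in this age group on the 4-week course. The nearest figure, in 8.1, is a general upper value of 5% for listed side effects in adults and older children. It does not apply directly here, so no count of affected children is offered.

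**The case against.** The case against is substantial, and most of it limits how far the point reaches.

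- **Rescue treatment is not blocked.** A reader might infer that 5.4 steers an emergency team away from life-saving steroid. The text does not support that. The parent's question arises only after a clinician has chosen a steroid, the rule names oral or inhaled products and does not expressly reach an injection, and the physician may proceed for medical reasons. A suspected adrenal crisis is plainly such a reason. What stands is that 5.4 leaves this to inference, and that oral steroid cover falls squarely within the non-steroidal step.
- **There may be a route to the outside clinician.** Section 6.11 says that after an SAE providers are unblinded and the child receives all necessary treatment; under 8.1 an adverse event leading to hospitalization is generally an SAE. This could convey the information. But the timing is not stated, the providers may be those at the study site, and the step follows the event.
- **The warning may be narrower than it looks.** In the Safety text, the phrase about such patients has no clear antecedent. It may mean all treated children or only those already suppressed. On either reading the family cannot know which children are suppressed when illness strikes, so the alert is still useful.
- **Family materials were not seen.** The consent form was removed from the supplied text, and the parent education promised in 5.4 was not supplied. Either may contain a full sick-day instruction. This stands, and it rules out any claim that families receive no such instruction.

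**Conclusion.** The point holds as a wording gap between the hazard in Section 7 and the parent rule in 5.4. Both parent actions depend on an oral or inhaled steroid being prescribed, the first is to seek an alternative, and no exception exists for suspected adrenal insufficiency or steroid cover. The supplied text does not have parents warn an outside clinician of possible adrenal suppression during acute illness or surgery.

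This is a cheap safety improvement. Two stronger conclusions should not be drawn. One is that the plan lacks adrenal safeguards: it has pre-dose and post-treatment cortisol testing, weekly contact on drug, SAE procedures and a route to endocrinology. The other is that families are left uninstructed, which cannot be judged without the consent form and education material. The verdict assumes only that 5.4 means what it says and that those unseen materials do not already settle the matter. If they do, the remaining task is to make 5.4 agree with them.

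**What to change.** First check the consent form and parent education material. Then add two provisions to 5.4 and align all three:

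1. From the first dose until the post-treatment morning cortisol is confirmed normal or endocrinology clears the child, for significant acute illness or any surgery, parents tell the treating clinician that the child is in a blinded megestrol trial and may have adrenal suppression. They also call the study team promptly, and seek emergency care if adrenal symptoms appear.
2. The non-steroidal step does not apply to treatment of suspected adrenal insufficiency, or to steroid cover that the treating physician judges necessary.

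The medical monitor and a pediatric endocrinologist should confirm the wording. No new recording rule is needed: 5.4 already has prescribed steroids reported, and 6.11 already has concomitant medications recorded at every clinic visit and tele-visit.

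The cost is a short amendment, a handout for both arms (up to the 72 families planned for recruitment in 4.3) and some extra calls. It adds no visits, tests, participants or routine unblinding. The downside is occasional steroid cover in a placebo child. Section 5.1 attributes megestrol's appetite effect probably to its glucocorticoid action, so such cover could touch the primary outcome; the existing 5.4 reporting would make it visible at analysis.

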
During the iKanEat protocol, we expect the child to lose weight during weeks 10-14 as the children taper off the tube. We inform parents of this expected weight loss and monitor the children closely. Despite this, in the previous trial there were instances of parents withdrawing their children during this weight loss period despite the physician guidance that the weight loss was expected and safe. It is critical that we learn more about this stressful period of the iKanEat protocol so we can better help parents through this transition. The current study design will allow us to learn more about how and when parent stress changes throughout the protocol in order to target supplemental treatment efforts related to parent stress.

Quality of Life.

Our most recent study (HD066629) also examined the role of pain and quality of life in tube weaning. Findings demonstrate improvement in pain symptoms ($t = 1.85$, $p = .006$) and in several areas of quality of life (i.e., growth and development, $t = -2.285$, $p < .05$; behavior, $t = -2.376$, $p < .05$; general health perceptions, $t = -2.232$, $p < .05$; parental impact: emotional and time, $t = -3.718$, $p < .005$) in the transition from tube to oral feeding.(11) In the current protocol we will assess whether successful transition to oral feeding has an effect on parent and child quality of life.

Remote Interventions.

CONFIDENTIAL

This material is strictly confidential and is intended solely for the guidance of clinical investigation. Do not disclose or use except as authorized in writing by the study sponsor

Our team has extensive experience delivering multidisciplinary feeding team clinical visits via interactive televideo. These visits are delivered as part of routine feeding team care in our clinic, and include both new patient visits and return patient visits. This clinical experience will serve our team well regarding the current scope of work.

Gut Microbiota

The gut microbiota refers to the species of bacteria living in the gut, and plays an essential role in digestive and immune function. Little is known about the effect formula feeding has on the microbiome, and the effects of transitioning from tube feeds to oral feeding. In the current protocol, we will assess whether successful transition to oral feeding has an effect on the gut microbiota.

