5.2 Treatment Regimen

Megestrol will be dosed based off their weight at the Week 10 visit, and dose will be rounded to the nearest 0.1 ml. Megestrol will be dosed at 6 mg/kg/d at weeks 10-11, at 4 mg/kg/d at week 12, at 2 mg/kg/d at week 13, and fully tapered at the end of week 13.

Equal doses will be taken twice daily. Subjects will be given instructions on when to take the medication and what to do if they miss a dose. If it has been < 6 hours since missing the dose, they should take the dose as soon as they remember. If it has been ≥ 6 hours since missing the dose, they should skip the dose. Subjects will be asked to document any skipped doses and report those to the study team at their next visit.

If a participant is removed from the study while taking the study drug, we will follow the drug tapering plan based on what day they are in the treatment regimen:

- Day 1-14 Drug can be stopped at current dose.
- Day 15-18 Continue 4 mg/kg for a total of 3 days. Decrease to 2 mg/kg for 3 days and then stop.
- Day 19-21 Decrease to 2 mg/kg for 3 days and then stop.
- Day 22-23 Continue 2 mg/kg for a total of 3 days and then stop.
- Day 24-28 Stop drug.

Regardless of when the drug is stopped, a morning cortisol lab value will be taken 5 days after the final dose of study drug.

CONFIDENTIAL

This material is strictly confidential and is intended solely for the guidance of clinical investigation. Do not disclose or use except as authorized in writing by the study sponsor

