6.11 Clinic Visit 4 (Week 24)

Participants will return to clinic to complete vital signs and measures (PIP, ITQOL or CHQ, RAND SF-36, PedsQL) and schedule three 24 hr Dietary recall phone calls over the coming week. Participants will bring in a frozen stool sample. Families will be encouraged to contact team members with questions or concerns at any time throughout the study period.

At every clinic visit and tele-visit we will record and evaluate concomitant medications. Also, if any safety concerns are noted at any clinic or tele-visit, additional visits may occur. Should any clinical concerns be noted, appropriate medical/clinical treatments will also occur as necessary. If any serious adverse events occur (as outlined elsewhere), providers will be unblinded to the subject's group, the subject will be removed from the study and patients will receive all necessary treatment clinically.

7 Statistical Plan

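### The primary efficacy test of megestrol uses a protocol-compliant set selected after randomization, and no analysis is assigned to all randomized children

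*Combined protocol and SAP*

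**What the plan says.** The unnumbered paragraph Population(s) for Analysis, late in section 7, sets the order of analyses: "Our primary analysis will focus on a protocol-compliant population, but we will secondarily also analyses the all-treated population, as described below". Three sets are then defined. The all-randomized set takes in every child allocated to an arm, dosed or not. The all-treated set keeps the children who took one dose or more. The third set is narrower and is the one used for the primary analysis: "Protocol-compliant population: Any subject who was randomized and received the protocol required study drug exposure and required protocol processing".

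The first has no analysis attached to it anywhere. The third gives no exposure threshold and does not say what protocol processing means. The sentence does not name Aim 1, but Aim 1 is the primary aim (section 2). Neither its methods (section 7, Planned Analyses) nor the Study Summary names another population. Hypothesis 1 is superiority: "Children randomized to the megestrol group will be significantly more successful in making the transition to oral feeding".

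Randomization follows Clinic Visit 1 at week 0 (section 6.2). The first dose comes at week 10 at the earliest, once a normal morning cortisol is confirmed (section 6.4). Section 4.4.2 seeks the diet recall from children who withdraw, so that the primary endpoint is known for them too.

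**The concern.** Randomization makes the arms comparable at week 0. A set defined by what happens afterwards need not be comparable, and the documents describe exits that can be linked to outcome:

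- Section 1.3 expects weight loss in weeks 10-14 and reports that "in the previous trial there were instances of parents withdrawing their children during this weight loss period". Those weeks overlap dosing in weeks 10-13.
- Section 6.11 says that after a serious adverse event "the subject will be removed from the study and patients will receive all necessary treatment clinically".
- Section 5.3 allows withdrawal for persistent missed doses.

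Section 5.2 also plans for exits during dosing: "If a participant is removed from the study while taking the study drug, we will follow the drug tapering plan". Appetite, weight and side effects may differ by arm once dosing starts, so blinding does not make these exits neutral.

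Sections 1 and 1.3 report that every child who completed the previous trial reached full oral feeding. Completion is not the same as compliance, and the outcomes of non-completers are not given. Still, any failures in that trial could only have been among non-completers. If the pattern recurs, the compliant set could drop the children who carry the treatment contrast.

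Not every exit selects in this way. The week-10 cortisol precedes the first dose, so it cannot select through a drug effect. A child removed after an abnormal week-14 cortisol has already had the full course, and is excluded only if the undefined processing criterion is read that way. A fully dosed child who still needs the tube (section 3.3, Tube Feeding Parent Report) may stay in the set.

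**Working it through.** **Inputs.** Section 7.1: 90% success on megestrol, with an odds ratio (placebo to megestrol) of .21 for 72 children and .18 for 60. Section 5.3: 1:1 allocation, so 36 or 30 per arm. Alpha is not stated for Aim 1; two-sided .05 is assumed. Exclusion rates are not given and are assumed below.

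**Placebo rates.** The megestrol odds are .9/.1 = 9.

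- OR .21: odds 1.89, rate 1.89/2.89 = .654.
- OR .18: odds 1.62, rate 1.62/2.62 = .618.

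**The plan's power.** A logistic-regression approximation gives power = Φ(|ln OR| × √(N × p̄(1−p̄)/4) − 1.96).

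- N = 72, p̄ = .777: 1.561 × 1.766 − 1.96 = .80, power .787.
- N = 60, p̄ = .759: 1.715 × 1.656 − 1.96 = .88, power .811.

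Both are within two points of the stated .80.

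**Method for the illustrations.** In each arm, successes are binomial(n, p). A fraction f of failures, and g of successes, leaves the set. The retained counts are compared with a pooled two-proportion z-test (no continuity correction, |z| > 1.96, no covariates), by exact enumeration. With no exclusions this test has power .75 (30 per arm) and .73 (36 per arm). That is the baseline here; its distance from .80 reflects the choice of test and is not part of this point.

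**Effect on the odds ratio.** With g = 0, the expected OR in the compliant set is the true OR × (1 − f_megestrol)/(1 − f_placebo). Equal f leaves it unchanged.

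**Power with the plan's effect present (g = 0):**

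| Failures lost, megestrol / placebo | OR (30 / 36 per arm) | Power (30 / 36 per arm) |
|---|---|---|
| none | .18 / .21 | .75 / .73 |
| 10% / 10% | .18 / .21 | .72 / .70 |
| 25% / 25% | .18 / .21 | .66 / .64 |
| 20% / 40% | .24 / .28 | .47 / .44 |
| 40% / 20% | .135 / .158 | .77 / .76 |

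For example, .18 × .8/.6 = .24 and .18 × .6/.8 = .135.

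**Type I error with no true effect (75% success in both arms):**

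| Lost, megestrol / placebo | 30 per arm | 36 per arm |
|---|---|---|
| 20% / 5% of all children, regardless of outcome | .051 | .051 |
| 20% / 20% of failures | .051 | .052 |
| 30% / 20% of failures | .055 | .057 |
| 40% / 20% of failures | .070 | .074 |
| 60% / 20% of failures | .146 | .164 |
| 40% / 20% of failures and 20% / 10% of successes | .056 | .058 |
| 60% / 20% of failures and 20% / 10% of successes | .107 | .123 |

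**In children.** With 36 per arm there are .25 × 36 = 9 expected failures per arm. Losing 40% / 20% of them is 3.6 + 1.8 = 5.4 of 72 (7.5%); 60% / 20% is 5.4 + 1.8 = 7.2 of 72 (10%). With 30 per arm the totals are 4.5 and 6 of 60, the same percentages. These totals are below the 20% drop-out allowed in section 4.3.

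**The case against.** **All-treated is planned and would remove most of the selection.** This largely stands as an argument about the remedy. Before the first dose only the pharmacy knows the allocation (sections 5.3 and 5.6), so loss up to that point should not depend on arm. All-treated would be an acceptable minimum. But it is secondary: if the two analyses disagree, the plan lets the unprotected one decide.

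**Analysing everyone randomized costs power, and the cost can be understated.** This stands. A child who leaves before week 10 never reaches the tube taper, so assuming the placebo-arm success rate for such children is favourable. If 20% never start drug, all-randomized power is .51 / .49 (30 / 36 per arm) at the placebo rate, about .46 / .45 if they succeed 30% of the time, and .43 / .41 if none succeed. All-treated power is .66 / .64.

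**The larger scenarios have no support in the documents.** True. Mild imbalance gives .055 to .074, and nothing shows that losses would be confined to failures or unequal between arms. The figures show what the design cannot exclude; they do not predict what will happen.

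**At 30 per arm, drop-out may be counted twice.** Sections 4.3 and 7.1 treat 60 as what remains of 72, whereas the Study Summary and section 3.1 give 60 as the number of subjects, with section 3.1 randomizing 30 to each arm. The base is ambiguous; the 36-per-arm figures avoid the problem and lead to the same conclusion.

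**Some early stoppers may count as compliant.** Required exposure is undefined, so a child who stops in the last days of the course might qualify. That supports defining the term.

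**Conclusion.** The concern holds. As written, the main efficacy conclusion would come from a comparison that randomization does not protect, in a set whose membership criteria are left to judgement. This follows from the text and needs no calculation.

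The numerical consequence cannot be known from the documents, and its direction is open. A real benefit is partly hidden if more placebo failures leave the set, and benefit is overstated if more megestrol failures leave. Loss unrelated to outcome, or equal loss of failures, costs power only. Under the assumed rates, unequal loss of failures within the planned drop-out takes type I error from about .05 to between .055 and .164, or cuts power from .75 / .73 to .47 / .44. These figures assume two-sided .05 and a test without the site, sex, age and interaction terms of the planned model. The point should be settled before unblinding.

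**What to change.** In Population(s) for Analysis:

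1. Make all-randomized the primary set for Aim 1, analysed by allocated arm and using the week-24 recalls sought under section 4.4.2, with all-treated as the first sensitivity analysis. At minimum, make all-treated primary and label it modified intention-to-treat.
2. Keep the protocol-compliant analysis as supportive, and define required drug exposure and required protocol processing in the text before unblinding.
3. Prespecify one rule for outcomes still missing after the section 4.4.2 efforts, and a sensitivity analysis under another. Multiple imputation from earlier recalls, and counting missing as not transitioned, are two candidates. A child who leaves before week 10 may have only a baseline recall, so the imputation model must say how such children are handled.
4. State the power under the rule chosen.

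The cost is wording plus power; no new type of data is needed. If 5 / 10 / 20% never start drug and succeed at the placebo rate, with all outcomes known, all-randomized power is .69 / .63 / .51 with 30 per arm and .67 / .61 / .49 with 36. For all-treated it is .73 / .71 / .66 and .72 / .69 / .64. Counting 10% / 20% missing as failures gives .57 / .43 with 30 per arm and .55 / .41 with 36. The missing-data cost shrinks as more recalls are recovered from withdrawn children.
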